9. COMPENSATION

Will participants be compensated for participation? Yes

Subjects will receive monetary reimbursements for completion of the main experimental sessions. Subjects will be compensated per visit for their time in the form of a single check that will be mailed upon completion or withdrawal from the study. There is no compensation for the screening session (Visit 1) because subjects will be receiving medical information from all of the screening tests free of charge. This information will be provided upon completion of the study. Subjects will be compensated for any visit that they attempt to complete; however, they will not be compensated if they skip a visit altogether. For example, if they attempt to complete the baseline MRI (Visit 4) but ultimately cannot go through with the procedures (e.g., due to claustrophobia), they will still be compensated for Visit 4; however, since they will not have completed a baseline visit, they will not be scheduled for the follow-up MRI (Visit 9) and will receive no compensation for that visit.

Compensation does not include travel time (we will compensate subjects for their travel if they wish at the current IRS approved mileage rate). If a subject withdraws or is withdrawn from the study, they will receive any health information collected and will be compensated for the study visits that they have already completed up to the time of withdrawal. Compensation is based on completion of study visits, not individual procedures. Subjects will be compensated for completing the majority of procedures in a visit. If a subject does not complete a visit at baseline, that visit will not be scheduled for follow-up and no compensation will be given for the follow-up visit. A table outlining the total compensation for each visit is presented below.

	Visit #	Purpose	Duration	Total
Screening	Visit 1	Informed Consent & Screening Measures	2 hr	No compensation Subjects receive free health information
g e	Visit 2	Vascular Function	3 hr	\$30
Baseline Testing	Visit 3	Cognitive Function	1.5 hr	\$22.50
	Visit 4	Neuronal Function/ Start Intervention	2 hr	\$30
n	No Visit	Check-In	10 min	\$9.00
Intervention Period	Visit 5	Check-In	0.5 hr	\$9.00
ver eric	No Visit	Check-In	10 min	\$9.00
P	Visit 6	Check-In	0.5 hr	\$9.00
-	No Visit	Check-In	10 min	\$9.00
Follow- Up Tasting	Visit 7	Vascular Function	3 hr	\$30
	Visit 8	Cognitive Function	1.5 hr	\$22.50
	Visits 9	Neuronal Function	2 hr	\$30
	Total Compen	\$210		

Compensation Schedule

10. **DATA**

Will subjects be anonymous to the researcher? No.

If subjects are identifiable, will their identities be kept confidential? (If yes, please specify how) All subject identifies and records will remain strictly confidential. Individual subject data will be coded and will not be associated with subject name. Documents that contain subject identifies (e.g., signed informed consent) will be kept in a separate locked filing cabinet. A list of names and participant numbers will be encrypted and stored on a password protected computer. This list will be kept for 5 years after study completion, after which it will be permanately deleted. All information obtained by the NMPCC, including electronic medical records, will be stored on a HIPAA compliant database.

How will data be stored and kept secure (specify data storage plans for both paper and electronic files. For guidance see http://www.udel.edu/research/preparing/datastorage.html)

Physical data will be stored in a locked file cabinet in the PI's lab space and will only be accessible by members of the research team. Physical data that are transcribed into an electronic database, and electronically captured data will be kept on a password protected laboratory server that is maintained by the University of Delaware. Electronic data will be periodically backed-up onto an external hard drive that will be kept in a locked office space. All of the ultrasound images and files generated by the SphygmoCor and RespirAct devices will be coded with an identification number and will not contain the name of the subject. The names of subjects will not be identified in any publication arising from these studies. Only the PI and research staff will have access to data from this study. With subject consent, biological samples (plasma/serum, peripheral blood mononuclear cells) will be kept for retrospective analyses related to aMCI and physiological function (this will not be conducted without IRB approval).

How long will data be stored? All data will be stored in a locked cabinet or a password protected computer indefinitely.

Will data be destroyed?
VES X NO (if yes, please specify how the data will be destroyed)

Will the data be shared with anyone outside of the research team? \Box YES **X**NO (if yes, please list the person(s), organization(s) and/or institution(s) and specify plans for secure data transfer)

How will data be analyzed and reported?

To determine if pre-intervention differences exist between groups, subject characteristics (e.g. total body fat, fasting blood glucose, etc.) will be compared between the two groups using unpaired t-tests. If assumptions of normality are met, separate linear regression models will be fit to compare NR vs. placebo (independent variable) with respect to change (baseline vs. week 12) for each of the outcome variables. Linear regression methods will be used to determine the association between/among changes in the primary or secondary outcomes in response to NR supplementation (e.g., to examine the association between changes in cognitive function and changes in arterial stiffness or cerebrovascular function). If assumptions of normality are not met, alternative strategies will be used, including transformation of variables, generalized linear mixed models, and non-parametric regression. To account for the blocked randomization scheme, indicator variables for block assignment will be included in the model as appropriate. To account for multiple testing of primary outcomes of interest in response to treatment, a Hotelling's T test will be used. If this multivariate test is significant then individual outcomes will be compared between groups at an alpha level of 0.05. Secondary outcomes (brain blood flow and blood pressure/arterial stiffness) will be assessed similarly with an adjusted alpha level of 0.0125. All tertiary outcomes will be considered more exploratory for future hypothesis testing. Given the design, treatment conditions and assessment protocols, we anticipate missing data (due to subject dropout, missed data collections, etc.) to be at least missing at random (MAR), if not missing completely at random (MCAR). Based on my pilot study, we do not expect the assigned treatment condition (NR or placebo) to influence whether a subject opts to continue with the study. Assuming missing data that are MAR or MCAR, a linear model or generalized linear model would vield valid inference.

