PRIMARY & SECONDARY OUTCOMES

All experimental visits will be performed in the PI's Laboratory unless otherwise indicated. An optional snack will be offered following all experimental visits in which fasting is required.

VISIT 2 & 7: VASCULAR FUNCTION (NOVA Lab; 3 hours each)

Subjects will be instructed to refrain from taking over the counter medications for 48 hours, vigorous aerobic exercise and alcohol for 24 hours, and to fast (no food, supplements or caffeine) for \geq 12 hours before testing.

- Height and body mass: Subject height and body mass will be measured using a physician's scale.
- Arterial Stiffness Assessments
 - Pulse Wave Velocity (PWV). Carotid-to-femoral PWV (a measure of aortic stiffness) will be assessed non-invasively using sequential transcutaneous tonometry of the carotid and femoral arteries (SphygmoCor, AtCor Medical). The time delay (transit time) between the foot of pressure waves obtained at each location will be determined using the R-wave of an ECG recording taken during the tonometry procedure as a timing reference. PWV will be calculated as the distance between measurement sites divided by the transit time of the arterial pulse wave.
 - Pulse Wave Analysis (PWA). Central hemodynamic properties, including the central pulse pressure (PP), augmentation pressure (AP) and augmentation index (AI) will be derived from the radial artery pulse wave using applanation tonometry.
 - Carotid Artery Compliance. Carotid compliance (a measure of large artery distensibility) will be measured non-invasively using high-resolution ultrasonography of one carotid artery and applanation tonometry of the opposite carotid artery (SphygmoCor, AtCor Medical). Compliance will be calculated as the change in carotid diameter for a given change in pressure as described previously by our laboratory.

Cerebrovascular Function Assessments

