- Wechsler Visual Reproduction Test (I and II). This test assesses visuoconstructional and visual memory function. The subject will be presented with a series of complex line drawing and will be asked first to copy the drawing onto a piece of paper, then re-draw the picture from memory following a 20-minute delay. Drawings will be scored for accuracy and correct placement of picture elements. This test must be completed in-person, and will be administered during Neuronal Function visits #4 and #9.
- **NIH Toolbox** (This test must be completed in-person, and will be administered during Neuronal Function visits #4 and #9).
 - Attention. Attention will be measured by the NIH Toolbox Inhibitory Control and Attention Test. The Flanker task measures both a participant's attention and inhibitory control. The test requires the participant to focus on a given stimulus while inhibiting attention to stimuli (fish for ages 3-7 or arrows for ages 8-85) flanking it. Sometimes the middle stimulus is pointing in the same direction as the "flankers" (congruent) and sometimes in the opposite direction (incongruent). Scoring is based on a combination of accuracy and reaction time.
 - Episodic Memory. Episodic Memory refers to cognitive processes involved in the acquisition, storage and retrieval of new information and will be measured with the NIH Toolbox Picture Sequence Memory Test. The Picture Sequence Memory Test is a measure developed for the assessment of episodic memory. It involves recalling increasingly lengthy series of illustrated objects and activities that are presented in a particular order on the computer screen. The participants are asked to recall the sequence of pictures that is demonstrated over two learning trials; sequence length varies from 6-18 pictures, depending on age. Participants are given credit for each adjacent pair of pictures (i.e., if pictures in locations 7 and 8 and placed in that order and adjacent to each other anywhere such as slots 1 and 2 one point is awarded) they correctly place, up to the maximum value for the sequence, which is one less than the sequence length (if there are 18 pictures in the sequence, the maximum score is 17, because that is the number of adjacent pairs of pictures that exist).
 - Working Memory. Working Memory refers to a limited-capacity storage buffer that becomes

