 - Metal: The MRI scanner produces a constant strong magnetic field, which may cause any metal implants, clips, or implanted medical devices within your body to shift position or malfunction. You will not be allowed to participate in this study if you have any implanted metal, clips or devices. You will be screened to make sure that it is safe for you to enter a strong magnetic field. Please provide us with as much information as you can, for example if you had surgery in the past, so that we may decide whether it is safe for you to be a participant. Metallic objects brought into the MRI environment can become hazardous projectiles and can also interfere with the data quality. To minimize this risk, metal earrings, other piercings, necklaces and any other metal in contact with your body must be removed prior to the study. You must also remove all items from your pockets, including coins, electronics (including cell phones and hearing aids) and wallets. You must remove belts with metal buckles, and you may be asked to change into a gown that we will provide if your clothing contains significant metal, including metal underwire bras.
 - Inner ear damage: MRI scanning produces loud noises that can cause damage to the inner ear if appropriate hearing protection is not used. Earplugs and/or headphones will be provided to protect your ears.
 - Claustrophobia: When inside the MRI scanner, the "bore" of the scanner will surround the part of the body that is being scanned. In the case of fMRI, we are interested in brain activity, and the head will be centered inside a close-fitting scanning coil positioned in the bore of the scanner. If the subject feels anxious in confined, spaces they may not want to participate. If they are unsure, they can try the "mock" scanner at the MRI facility to evaluate their comfort level with the enclosed space of the magnet bore. If they decide to participate and begin to feel claustrophobic, they will be able to communicate with the research team via the intercom or the squeeze ball and the test will be discontinued.

Subjects who do not complete MRI testing will still be allowed to continue with the trial.

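### Section 9 cancels Visit 9 after a failed baseline MRI, although two in-person cognitive instruments are given at that visit; on a whole-visit reading, an exploratory scan costs obtainable week-12 scores

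*Combined protocol and SAP*

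**What the plan says.** Section 9 (Compensation) takes as its example a participant who tries the baseline MRI at Visit 4 and cannot complete it. That person is paid for Visit 4, but "since they will not have completed a baseline visit, they will not be scheduled for the follow-up MRI (Visit 9" and "and will receive no compensation for that visit". The next paragraph sets the unit of payment: "Compensation is based on completion of study visits, not individual procedures". It then turns the example into a general rule: "If a subject does not complete a visit at baseline, that visit will not be scheduled for follow-up".

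Section 6 (Procedures, Visits 4 & 9: Neuronal Function) puts more than the scan into those visits. For Visual Reproduction, and again for the NIH Toolbox, it says: "This test must be completed in-person, and will be administered during Neuronal Function visits #4 and #9". The same part of Section 6 classes all fMRI outcomes as exploratory, neither primary nor secondary.

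Section 8 (Risks and Benefits, MRI Scan) keeps the participant in the study: "Subjects who do not complete MRI testing will still be allowed to continue with the trial". The visit table in Section 6 still has that person coming to the laboratory at week 12 for Visit 7 (vascular testing).

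**The concern.** Two efficacy instruments share a visit with an exploratory scan, and Section 9 makes that visit depend on completing its baseline counterpart. If the rule means the whole visit, someone who cannot tolerate the scanner is not called back for Visual Reproduction or the NIH Toolbox. Section 6 does not describe either test as needing the scanner.

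The Study Design paragraph makes memory and other cognitive functions the efficacy question and requires all primary and secondary outcomes at baseline and week 12. Section 10 analyses the change between those two points, so a missing week-12 score means no change score. Section 10 also tests the primary outcomes jointly with Hotelling's T before testing them singly. The plan does not list the components of that test. If either instrument is one of them and the test uses complete cases (both are assumptions), the participant also leaves the joint test, even though CVLT III and Logical Memory scores exist.

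Section 6 does not say that the two tests are given at Visit 4 when the scan fails, so the baseline scores may be missing too.

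**Working it through.** The plan states no figure on this point, so the main check is of the text.

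**What the rule covers**

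1. The Section 9 example treats a failed MRI as an uncompleted baseline visit.
2. Its label for what is cancelled, the follow-up MRI with Visit 9 in brackets, could mean the scan alone or the whole visit.
3. The refusal of payment is for the visit, payment is by visit rather than by procedure, and the general rule says the visit is not scheduled. All three favour the whole visit.
4. Section 6 assigns the two instruments to Visits 4 and 9, in person only. It gives no other place or time for them if Visit 9 is not held.
5. Section 8 keeps the participant in the trial, so the week-12 scores could be obtained.

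**What one affected participant loses**

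- Cognitive instruments named under Visits 3 & 8: CVLT III, Logical Memory, Visual Reproduction and NIH Toolbox = 4. Given at Visits 4 and 9: 2 of the 4.
- Named memory tests: CVLT III, Logical Memory and Visual Reproduction = 3. Affected: 1 of the 3.
- Share of the target sample of 58 (Section 7): 1/58 = 1.7% for each of the two instruments.

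**Illustration for the trial**

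The documents give no rate of failed baseline scans, so the counts below are assumptions. With equal arms, the standard error of the arm difference grows by the factor √(58/n), where n is the number with change scores.

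| Participants lost (assumed) | n | √(58/n) |
|---|---|---|
| 0 | 58 | 1.000 |
| 1 | 57 | 1.009 |
| 2 | 56 | 1.018 |
| 3 | 55 | 1.027 |

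A wider assumed range of failure rates, 2% to 15% of 58 (about 1 to 9 people), gives 1/√(1 − 0.02) = 1.010 to 1/√(1 − 0.15) = 1.085. The upper end is unlikely, because Section 7 excludes claustrophobia and Section 8 screens for it and offers a mock scanner.

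Section 7 recruits 73 to reach 58, an allowance of 73 − 58 = 15 that includes experimental failure. Losses that fall within it could have no net effect on the target.

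**Payment**

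The schedule reproduces its own total: 2 × (30 + 22.50 + 30) + 5 × 9 = $210. Visit 9 accounts for $30. For 1 to 3 people that is $30 to $90 before mileage.

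**The case against.** The strongest reply is that Section 9 is a payment section and not the visit schedule. Its example speaks of the MRI, and the Section 6 assignment of the two tests is unconditional. Section 9 also says that doing most of a visit's procedures earns the payment. Visit 4 includes the screening form, the scan sequences, two sets of cognitive tests and the dispensing of capsules, so someone who fails only the scan might count as having completed it. This makes a scan-only reading possible but does not settle the matter. The sentence governs payment, and the section's own example still calls the failed MRI an uncompleted visit. If only the scan is meant, Section 9 wrongly denies payment for a visit the person attends, so the text needs correcting on either reading.

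A second reply is that Section 6 allows in-person cognitive testing at Visits 3 and 8, and that the Study Timeline lets visits be reordered and moved by up to 7 days. Neither provision moves these two instruments, which Section 6 assigns specifically to Visits 4 and 9.

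Third, the change score is lost through cancellation of Visit 9 only if baseline scores were obtained at Visit 4. That is correct, and the plan is silent on it. The remedy must therefore cover both visits.

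Fourth, the numbers are small, and Section 10 already anticipates some missed data collection. This stands and limits the weight of the point. It does not justify losing scores that are cheap to collect.

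**Conclusion.** The concern holds. Followed as written, and read at visit level, the Section 9 rule discards obtainable week-12 scores on two of four cognitive instruments for any participant whose baseline scan fails. It conflicts in effect with Sections 6 and 8.

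The size is modest: 1.7% of the target sample per affected participant on those instruments, and a standard error up to 2.7% larger if as many as 3 people are affected. That count is assumed, and the effect may be zero.

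No bias between arms is shown, because the trigger falls at Visit 4, when capsules are first handed out. No definite power loss is shown, and CVLT III and Logical Memory are untouched. Confidence is medium, because the scan-only reading cannot be ruled out. This is a cheap improvement that should be made, and it does not threaten the trial's validity.

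**What to change.** Reconcile Section 9 with Sections 6 and 8 in one statement, placed in the visit schedule and repeated under Compensation:

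> *An incomplete MRI at Visit 4 cancels only the follow-up scan. Visual Reproduction and the NIH Toolbox are given at Visit 4 whether or not the scan is completed. These participants attend Visit 9 for those tests and are paid for it.*

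The general rule in Section 9 then needs a matching exception.

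The cost per affected participant is the $30 Visit 9 payment, any mileage claimed ("we will compensate subjects for their travel if they wish at the current IRS approved mileage rate") and examiner time for a short test session. No test or visit is added to the planned schedule. The consent form was not available for this review. If it repeats the rule, its wording must change too.

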6. PROCEDURES

Study Design. A randomized, placebo-controlled, double blind, parallel group clinical trial will be conducted to assess the efficacy of 12-weeks of oral nicotinamide riboside capsules (NR; 500mg, 2x/day, trade name NIAGEN®, ChromaDex Inc., Irvine CA) for improving memory and other cognitive functions in adults with cognitive scores indicative of aMCI. Secondary outcomes will include measures of vascular/cerebrovascular and neuronal function and brain structure. This design and duration has been used previously to study the efficacy of interventions for improving vascular function in older adults⁷. Study participants and investigators involved in data acquisition and/or analysis will be blinded to treatment condition. All primary and secondary outcome measures will be made at baseline and after 12 weeks of treatment. Visits will take place in the Neurovascular Aging Laboratory (NOVA Lab) on the STAR Research Campus at the University of Delaware, with the exception of MRI measures which will be made at the UD Center for Biomedical Brain Imaging (CBBI). Details pertaining to the safety and toxicity of the intervention and rationale for the proposed frequency and duration are presented at the end of this section.

DETAILED OVERVIEW OF STUDY VISITS

PRE-SCREENING PHONE SCREENING

Prior to scheduling Visit 1 informed consent & screening, a member of the research team will complete a brief phone screen and will ask the subject the COVID-19 questionnaire in order to ascertain specific information regarding possible hospitalization as a result of COVID-19 diagnoses, and vaccination. If subject acknowledges any hospitalization as a result of COVID-19, the subject will be excluded and will not be permitted to enroll in the current study. If the subject discloses specific information as it relates to receiving the COVID-19 vaccine, the subject will not be permitted to participate in any data collection procedures until one week following any COVID-19 vaccination. These questions will also be asked during the week 10 phone check-in before scheduling week 12 visits.

VISIT 1: INFORMED CONSENT & SCREENING (2.0 hours)

Subjects will be instructed to fast for \geq 12 hours before testing

Informed Consent for participation in the clinical trial will be obtained by a trained member of the

	Week	Visit #	Duration	Location	Visit Description	Blood

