- APOE Genotype (Visit 1 only). Individuals with the E4 variant of the Apolipoprotein E (APOE) gene are at increased risk of developing late-onset Alzheimer's disease (AD)⁸. Because the APOE gene is also involved in the regulation of lipid metabolism, specific variants of this gene have been associated with increased risk for cardiovascular diseases. To ensure that APOE genotype does not confound any of our primary cardiovascular outcomes, and to ensure that subjects carrying the E4 variant are evenly distributed between the active and placebo arm of the study, we will isolate each subject's DNA and will determine their APOE genotype using PCR, prior to randomization. The results of this test will be made available to subjects, upon request, with a disclaimer that the results were generated in a non CLIA-certified laboratory for research purposes only.
- General blood chemistry. Includes a comprehensive metabolic profile, lipid profile, complete blood count (CBC) with differential, prothrombin time and partial thromboplastin time.
- Kidney and liver function. Because kidney and liver dysfunction could influence the metabolism and bioavailability of NR, markers of liver function (ALB, ALT, AST, ALP, total bilirubin (TBILI) and kidney function (blood urea nitrogen (BUN), creatinine (CRE), sodium, and potassium) will be measured prior to subject randomization.
- Vitamin B6, B12 and Folate. Known to influence memory.
- **Peripheral Blood Mononuclear Cells.** Required for assessment of NAD⁺ related metabolites and mitochondrial respiration.
- COVID Antibody. Because recent COVID-19 infection has been associated with increased incidence of stroke and other cardiovascular complications, we will test for the presence of COVID-19 antibodies at baseline and at the end of the study and will perform a sensitivity analysis at the end of the study to determine the potential confounding effect of previous COVID-19 infection on all study outcomes. This test will only be performed in individuals not vaccinated against the SARS-CoV2 virus.
- **Baseline Urine Sampling.** A midstream urine specimen will be collected into a clear container during the baseline laboratory visit, or at their local LabCorp patient service center and a complete urinalysis will be conducted. Urine samples will be collected after the early morning void has been discarded. Urinalysis will be repeated after the 12-week intervention period.

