- **Middle Cerebral Artery Screening:** A research team member will use a transcranial doppler ultrasound probe to examine the temporal window for screening of a visible middle cerebral artery. This is done during the screening visit to simplify the preparation of Visits 2 & 7. The results of this screening test will not impact eligibility for this study.

RANDOMIZĂTION (will occur after VISIT 1.1)

Randomization Procedures. Subjects who qualify for the study based on screening assessments will be randomly assigned by the study coordinator to receive either treatment A or treatment B. The identity of each treatment (i.e., NR or placebo) will be blinded by the manufacturer (ChromaDex, Inc.) and the blinding code will be sent to a member of the PI's department ([name]) who is unaffiliated with this study. [name] will enter the blinding code in a secure REDCap form that will remain hidden from the rest of the study team. The PI will be given a separate login ID and password to access this REDCap form and determine the assigned treatment condition of a subject in the event of an emergency (described below under serious adverse events). A blocked randomization scheme will be uploaded into REDCap by the biostatistician with block size (*b*) resulting in an imbalance of no more than 2 subjects (*b*/2) between group assignments. To address potential imbalance between key biological variables including sex (male vs. female) and APOEε4 status (carriers vs. non-carriers),

the blocked randomization scheme will be stratified such that participants within each strata will be block randomized to either placebo or NR.

Study Restrictions. All experimental visits will be conducted under overnight fasted conditions (no meal within ~12 hours of testing) with the exception of cognitive function and MRI sessions. Participants will be asked to discontinue use of any vitamin B₃-containing supplements (i.e., nicotinamide, niacin, nicotinic acid, nicotinamide riboside, nicotinamide mononucleotide) 2 weeks prior to and throughout participation in the study. Subjects will be asked to refrain from non-prescription medications for 48 hours; alcohol and exercise for 24 hours, caffeine for 12 hours prior to all study visits as these are factors known to modulate vascular function as well as circulating biomarkers of interest. If subjects receive the COVID-19 vaccine, they will not perform any experimental visit until at least one week following vaccination.

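### The outcome models compare arms on raw change, omit each outcome's baseline value and leave the design terms open; prespecifying baseline, sex and APOE4 is a cheap gain in precision

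*Combined protocol and SAP*

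**What the plan says.** The analysis is described in section 10 (Data), under the question on how data will be analysed and reported. There, "separate linear regression models will be fit to compare NR vs. placebo (independent variable) with respect to change (baseline vs. week 12" for each outcome variable. The only other term mentioned is for the design: "To account for the blocked randomization scheme, indicator variables for block assignment will be included in the model as appropriate". No rule says when those indicators enter, and no model anywhere includes the outcome's baseline value, sex or APOE4 status.

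Primary outcomes first pass a Hotelling's T test, and "If this multivariate test is significant then individual outcomes will be compared between groups at an alpha level of 0.05". Secondary outcomes are handled in the same way at 0.0125.

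Three statements in section 6 (Procedures) bear on this:

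- Study Design: "All primary and secondary outcome measures will be made at baseline and after 12 weeks of treatment".
- Randomization Procedures: sex and APOE4 carrier status are the stratification factors, and "the blocked randomization scheme will be stratified such that participants within each strata will be block randomized to either placebo or NR".
- Visit 1.1: APOE is genotyped before randomisation, with the stated aim "To ensure that APOE genotype does not confound any of our primary cardiovascular outcomes" and to spread carriers evenly over the arms.

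**The concern.** Regressing change on arm alone fixes the slope on baseline at 1. When the true slope is lower, as is usual for a measure with test-retest noise, the comparison carries avoidable variance. The target is 58 participants (section 7), and the value that would remove this variance is already collected.

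The design terms are also undefined. A block could mean an individual randomisation block or one of the four sex-by-APOE4 strata. These are different models, and two analysts could each follow the text and fit a different one. The Study Design paragraph says "Study participants and investigators involved in data acquisition and/or analysis will be blinded to treatment condition". That lowers the risk of a choice favouring one arm, but it does not say which model is to be fitted.

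**Working it through.** **Inputs from the documents.** Target 58 (section 7), taken as 29 per arm. Blocks of 4, inferred from the imbalance limit of 2, described as half the block size (section 6). Alpha 0.05 for individual primaries and 0.0125 for secondaries (section 10), taken as two-sided. No power, effect size, SD or correlation is given, so the plan has no power figure to reproduce.

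**Assumed inputs, shown as ranges.** r = 0.4 to 0.9; k = week-12 SD divided by baseline SD = 0.9, 1.0 or 1.1.

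**Step 1: variance ratio, baseline-adjusted against plain change.** Gross ratio = k²(1 − r²) / (1 + k² − 2rk). With k = 1 this is (1 + r)/2.

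**Step 2: cost of the extra terms.** Multiply by 1 + 1/54 for estimating the slope and by about 1.003 for sex and APOE4. Example, k = 1 and r = 0.5: 0.75 × 1.0185 × 1.003 = 0.766, a net cut of 23%.

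| r | k = 1.0 | k = 0.9 | k = 1.1 |
|---|---|---|---|
| 0.4 | 28% | 36% | 22% |
| 0.5 | 23% | 32% | 16% |
| 0.6 | 18% | 27% | 11% |
| 0.7 | 13% | 23% | 6% |
| 0.8 | 8% | 19% | 1% |
| 0.9 | 3% | 17% | −2% |

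The gross ratio reaches 1 where the true slope rk is 1. The net loss there is 1.0185 × 1.003 − 1 = about 2.2%, the worst case at 58 analysed. A simulation with blocks of 4 in four strata (8,000 runs per case) agreed with these cuts to within about 2 points. Mean estimates were within 0.01 of zero under no effect.

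**Step 3: effective sample size and single-outcome power.** Effective size is 58 divided by the net ratio. Power uses the noncentral t with 53 df, at the effect that gives plain change 80% power with 56 df (0.75 SD of change).

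| k | Effective size, r = 0.4 to 0.9 | Power |
|---|---|---|
| 1.0 | 81 to 60 | 91% to 81% |
| 0.9 | 91 to 70 | 94% to 87% |
| 1.1 | 74 to 57 | 89% to 79% |

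At alpha 0.0125 the same calculation (80% on change at 0.90 SD, k = 1) gives about 91%, 86% and 81% at r = 0.5, 0.7 and 0.9.

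**Step 4: source of the gain.** With k = 1, baseline alone cuts 28.7% to 3.2%, against 28.5% to 3.0% for the full model. If sex and APOE4 are not prognostic, they change the cut by 0.0 to −0.4 points. If each explains 5% of variance at both visits, they change it by +0.4 to −0.4 points. Their role is to match the analysis to the stratified design. In a separate simulation where both predicted change, type I error with baseline was 0.038 to 0.043 without them and 0.045 to 0.052 with them.

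**Step 5: the two readings of block.** 58/4 = 14.5, so about 16 individual blocks once four strata leave some incomplete. That takes residual df from 56 to 41. Strata need 3 indicators. On the strata reading, the gains above hold to within about 1 point. No extra gain is claimed against individual-block indicators.

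**Step 6: with the gate.** Simulated chance that a given primary is declared, with Hotelling's T on change, then individual tests on change / adjusted. Assumptions: 0.4 cross-trait correlation, equal effects, 80% gate power. The number of primaries is also assumed; section 6 describes three memory tests and seven NIH Toolbox tests.

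| Primaries | r = 0.5 | r = 0.7 | r = 0.9 |
|---|---|---|---|
| 3 | 47 / 54% | 47 / 51% | 48 / 48% |
| 7 | 31 / 37% | 30 / 34% | 31 / 31% |
| 10 | 25 / 29% | 25 / 27% | 25 / 26% |

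Family error under the complete null was 4.2% to 5.3% (change) and 2.9% to 5.3% (adjusted).

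**Step 7: adjusting the gate too.** Putting all primary baselines, sex and APOE4 into the Hotelling's test moved its power as follows (change / adjusted, r = 0.5, 0.7, 0.9): three primaries 80/84, 81/81, 82/79; seven 81/80, 82/77, 80/74; ten 79/70, 80/70, 80/66.

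**The case against.** The best reply is that nothing here is wrong. Raw change is valid under randomisation, and a one-paragraph answer on an ethics form that is silent on baseline adjustment does not exclude it. That stands, and it is why this is an improvement and not an error.

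The single-outcome power figures also flatter the operational benefit, because the gate comes first and stays on change. That stands too: the two-step gain is 0 to 7 points, and 1 to 4 with ten primaries. Narrower intervals are obtained regardless.

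Blocks are nested in strata, so a full set of block indicators already absorbs sex and APOE4. This is correct, and the stratum terms should therefore replace the block indicators and not join them. What remains open is which meaning of block applies and when the terms enter. The APOE statement also refers to cardiovascular outcomes, so it lends little support for the cognitive primaries. The case rests on the stratification.

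Not every outcome will have 58 analysed. Cerebrovascular reactivity needs a usable temporal window, and the NIH Toolbox is given at the MRI visits. With an assumed 35 analysed, the worst loss is (1 + 1/31) × 1.003 − 1 = about 3.5%. The conclusion survives.

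Finally, section 10 also leaves open what happens if normality fails. This change does not settle that.

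**Conclusion.** The concern holds as a cheap improvement that should be made. The plan leaves unused a baseline value it already collects and does not define its design terms. With 58 analysed, the net change in variance runs from a 36% cut to a loss of about 2% over r = 0.4 to 0.9 and SD ratios of 0.9 to 1.1. With equal SDs it is a cut of 28% to 3%. No single figure can be claimed for this trial, because r and the SD ratio are not given. With equal SDs the gain is clear at r of 0.5 to 0.7 and small near 0.9. Almost all of it comes from baseline. The chance of passing the Hotelling's gate does not change.

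**What to change.** In section 10, for each individual-outcome model, primary and secondary, prespecify week-12 value (or change) on treatment, that outcome's baseline value, sex and APOE4 carrier status. Use these terms in place of the block indicators and delete the qualifier that makes design terms discretionary. State that sex and APOE4 are included because randomisation is stratified on them. Keep Hotelling's T on change scores by default, and do not add all primary baselines to it unless the number of primaries is small. Keep unadjusted change as a sensitivity analysis.

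The cost is SAP wording before unblinding and 3 df per model. No new data are needed. No participants are lost, because change already requires a baseline and section 9 does not schedule a follow-up visit whose baseline visit was not completed. The downside is the loss of about 2% at 58 analysed where the true slope is near 1.
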